Appendix IV: Selected drugs known to be metabolized by CYP3A4

CYP3A4 INHIBITORS INDUCERS l Trade Name eric Name Trade Name Generic Name Trade Name Anti-arrhythmics: e.g. Cytadren Aminoglutethimide Anti-neoplastics: e.g. Docetaxel Taxotere Amlodarone Cordarone, Pacerone Gefitinib Cardizem, Dilacor XR Diltiazem Iressa Irlnotecan Camntosar $Q\mu_i,11_i <: l_i t1$ Cardioauin Antibiotics: e.g. Anti-virals: e.g. Anti-virals: e.g. Amprenavir Rifadin Agenerase Agenerase Rifabutin Amprenivir Mycobutin Indinavir Crixivan Rifampin Rifampin Rifadin Nelfinavir Viracept Ritonavir _Norvir Anticonvulsants: e.g. Cimetadine Tagamet Anxio\ytics: e.g. Carbamazapine Tegretol Valium Diazepam DHantin Phenytoin Zo!oft Sertraline Pentobarbital Nembutal Phenobarbital Luminal St. John's Wort Sandimmune H1mericum verforatum (2) Cyc\osporine Sandimmune y(::IQSp_(l·:ii:i Anti-infectives: e.g. Antibiotics: e.g. Erythromycin Erythrocin Ciprofloxacin Cipro, Ciloxan Clarithromycin Biaxin Tetracycline Sumycin Adoxa, Periostat Doxycycline Enoxacin Penetrex Nydrazid, INH Isoniazid Ketek Telithromycin Steroids: e.g. Imatinib Gleevec Estrogens, conjugated Premarin Estradiol C!imara Progesterone Crinone _ Haldol Haloperidol l_pr.!9£1"_... Diclofenac Cataflam, Voltaren Cardiovascular agents: e.g. Digitoxin Crystodigin Quinidine .G.<:1:r.<:i.i.9.g _i_f! Vasodi\ators: e.g. Anti-hypertensives: e.g. Cardene Nlcard ipine Cardene Nicardipine Calan, Chronovera Calan. Chronovera yera12:amil Verapamil Anesthetics: e.g. Anesthetics: e.i: Lidocaine Ketamine Xylocaine Xylocaine Di2rivan f.fOJJ().f()_l_ Lidocaine Anti-depressants: e.g. Nefazodone Serzone Nefazodone Serzone Sertraline A ti fUrtgaiil:.e.g. Cocaine Itraconazole Sporanox Ketoconazole Nizoral Lotrimin, Monistat Miconazole N..... Caffeine Ketoconazole o; ;;efrUft ; k (fi... Sildenafil ..."Y!.f! gra Albuterol \ Ventolin Carbamazapine 1....I _gretol Lovastatin Mevacor

When drugs classified as 'substrates' are co-administered with (Study Agent). there is the potential for higher concentrations of the 'substrate'. When (Study Agent) is co-administered with compounds classified as 'inhibitors', increased plasma concentrations of (Study Agent) is the potential outcome. The co-administration of inducers' would potentially lower plasma (Study Agent) concentrations.

Comprehensive list of drngs that may have potential interactions with CYP3A4

CYP3A4

| Substrates | | | |
|-------------------|------------------------------|--------------------------------|---------------------------|
| Albuterol | Docetaxel | Ketoconazole | Quetiapine |
| Alfentanil | Doxepin | Lansoprazole | Quinidine |
| Alprazolam | Doxorubicin | Letrozole | Rabeprazole |
| Amlodiplne | Doxycycline | Levomethadyl acetate | Repaglinide |
| Amprenavir | Efavirenz | hydrochloride | Rifabutin |
| Aprepitant | Eletriptan | Levonorgestrel | Rifampin |
| Aripiprazole | Enalapril | Lidocaine | Ritonavir |
| Atazanavir | Eplerenone | Losartan | Saquinavir |
| Atorvastatin | Ergoloid mesylates | Lovastatin | Sertraline Sibutramine |
| Benzphetamine | Ergonovine | Medroxyprogesterone Mefloquine | Sildenafi! |
| Bisoprolol | Ergotamine | Mestranol | Simvastatin |
| Bortezomib | Erythromycin | Methadone | Sirolimus |
| Bosentan | Escitalopram | Methylergonovine | Sufentanil |
| Bromazepam | Estradiol | Methysergide | Tacrolimus |
| Bromocriptine | Estrogens, conj., synthetic | Miconazole | Tamoxifen |
| Buprenorphine | Estrogens, conj., equine | Midazolam | Tamoxilen |
| Buspirone | Estrogens, conj., esterlfied | Miglustat | |
| Busulfan | Estrone | Mirtazapine | Telithromycin |
| Carbamazapine | Estropipate | Modafinil | Teniposide |
| Cerivastatin | Ethinyl estradiol | Monte!ukast | Terbinafine |
| Chlordiazepoxide | Ethosuximide | Moricizine | Tetracycline |
| Chloroquine | Etoposide | Nateglinide | Theophylline |
| Chlorpheniramine | Felbamate | Nefazodone | Tiagabine |
| Cisapride | Felodipine | Nelfinavir | Ticlopidine |
| Cita\opram | Fentanyl | Nevirapine | To\terodine |
| Clarithromycin | Flurazepam | Nicardlpine | Toremifene |
| Clobazam | Flutamide | Nifedipine | Trazodone |
| Clonazepam | Fosamprenavir | Nimodipine | Triazolam |
| Clorazepate | Fu\vestrant | Nisoldipine | Trimethoprim |
| Cocaine | Gefitinib | Nitrendipine | Trimipramine |
| Colchicine | Halofantrine | Norethindrone | Troleandomycin |
| Cyclophosphamide | Haloperido\ | Norgestrel | Vardenafil |
| Cyclosporine | Ifosfamide | Ondansetron | Venlafaxine |
| Dantrolene | Imatinib | Pac!itax.e\ | Verapamil |
| Dapsone | Indinavir | Pergolide | Vinblastine |
| Delayirdine | Irinotecan | Phencyclidine | Vincristine |
| Diazepam | Isosorbide dinitrate | Pimozide | Vinorelbine |
| Digitoxin | Isosorbide mononitrate | Piog\itazone | Zolpidem |
| Dihydroergotamine | Isradipine | Primaquine | Zonisamide |
| Diltiazem | ltraconazole | Progesterone | Zopic!one |
| Disoovramide | Ketamine | | 1 |

CYP3A4

| Inhibitors | | | |
|-----------------|-------------------|--------------------|---------------|
| Acetaminophen | Dıltıazem | Lovastatin | Progesterone |
| Acetazolamide | Disulfiram | Mefloquine | Propofol |
| Amioderone | Docetaxel | Mestranol | Propoxyphene |
| Amlodipine | Doxorubicin | Methadone | Quinidine |
| Amprenavir | Doxycycline | Methimazole | Quinine |
| Anastrozole | Drospirenone | Methoxsalen | Quinupristin |
| Aprepitant | Efavirenz | Methylprednisolone | Rabeprazole |
| Atazanavir | Enoxacin | Metronidazo!e | Risperidone |
| Atorvastatin | Entacapone | Miconazole | Ritonavir |
| Azelastine | Ergotamine | Midazolam | Saquinavir |
| Azithrornycin | Erythromycin | Mifepristone | Selegiline |
| Betamethasone | Ethinyl estradiol | Mirtazapine | Sertraline |
| Bortezomib | Etoposide | Mitoxantrone | Sildenafil |
| Bromocriptine | Felodipine | Modafinil | Sirolimus |
| Caffiene | Fentanyl | Nefazodone | Sulconazole |
| Cerivastatin | Fluconazole | Nelfinavir | Tacro!imus |
| Chloramphenico! | Fluoxetine | Nevirapine | Tamoxifen |
| Chlorzoxazone | Fluvastatin | Nicardipine | Telithromycin |
| Cimetadine | Fluvoxamine | Nifedipine | Teniposide |
| Ciorofloxacin | Fosamnrenavir | Nisoldioine | Testosterone |

| Cisapride | Glyburide | Nitrendipine | Tetracycline |
|-------------------|------------------|---------------|-----------------|
| Clarithromycin | Grapefruit juice | Nizatidine | Ticlopidine |
| Clemastine | I-Ialoperidol | Nortloxacin | Trany\cypromine |
| Clofazimine | Hydralazine | O!anzapine | Trazodone |
| Clotrimazole | Ifosfamide | Omeprazo\e | Troleandomycin |
| Clozapine | Imatinib | Orphenadrine | Valproic acid |
| Cocaine | Indinavir | Oxybutynin | Venlafaxine |
| Cyclophosphamide | Irbesartan | Paroxetine | Verapimil |
| Cyclosporine | lsoniazid | Pentamidine | Vinb!astine |
| Danazol | Isradapine | Pergolide | Vincristine |
| Delavirdine | Itraconazole | Phencyclidine | Vinorelbine |
| Desipramine | Ketoconazole | Pilocarpine | Zafirlukast |
| Dexmedetomidinc | Lansoprazole | Pimozide | Ziprasidone |
| Diazepam | Lidocaine | Pravastatin | _ |
| Diclofenac | Lomustine | Prednisolone | |
| Dihydroergotamine | Losartan | Primaquine | |

| Inducers | | | |
|-------------------|---------------|-----------|-------------|
| Aminoglutethimide | Nevirapine | Phenytoin | Rifapentine |
| Carbamazapine | Oxcarbazepine | Primidone | |
| Fosphenytoin | Pentobarbital | Rifabutin | |
| St. John's wort | Phenobarbital | Rifampin | |

(Adapted from Cytochrome P-450 Enzymes and Drug metabolism. In: Lacy CF, Annstrong LL, Goldman MP, Lance LL eds. Drug Infonnation Handbook 12TH ed. Hudson, OH; LexiComp Inc. 2004: 1619-1631.)

Potential Drug Interactions:

In vitro data indicate that sirolimus is an inhibitor for CYP2C9, CYP1A2, CYP2B6, CYP2C8, CYP2C19, CYP2D6, CYP2El, and CYP3A4. In animal studies, there were no GW786034-related effects on the activities of CYP1A, CYP2B, CYP2E, CYP3A, and CYP4A.

In vitro, the most potent inhibition was seen for the isoenzyme CYP2C9. Accordingly, the following medications which are substrates for CYP2C9 are PROHIBITED in subjects receiving sirolimus (the washout period is at the discretion of the clinician based on the pharmacokinetic properties of each individual agent):

- Anticoagulants: warfarin (therapeutic doses only)
- Oral hypoglycemics: glipizide, glyburide, tolbutamide, glimepiride, nateglinide
- Ergot derivatives: dihydroergotamine, ergonovine, ergotamine, methylergonovine
- Neuroleptic: pimozide
- Erectile dysfunction agents: sildenafil, tadalafil, vardenafil
- Antiarrhythmics: bepridil, flecainide, lidocaine, mexilitine, amiodarone, quinidine, propafenone
- Immune modulators: cyclosporine, tacrolimus, sirolimus
- Miscellaneous: theophylline, quetiapine, risperidone, tacrine, cloazapine, atomoxetine

Certain medications should be used with CAUTION due to the potential for alterations in the pharmacologic effects or increased adverse events secondary to the inhibition of multiple CYP enzymes by sirolimus. These medications include (but are not limited to):

• Antidepressants: amitriptyline, buproprion, fluoxetine, fluvoxamine, imipramine

- HMG co-reductase inhibitors: atorvastatin, fluvastatin, lovastatin, simvastatin
- Benzodiazepines: alprazolam, midazolam, triazolam, clorazepate, diazepam, flurazepam
- Calcium channel blockers: diltiazem, felodipine, nifedipine, nicardipine, nimodipine, nitrendipine, verapamil, amlodipine, nisoldipine, isradipine
- Angiotensin II blockers: losartan, irbesartan
- Beta blockers: carvedilol, metoprolol, propanolol, timolol
- Anticonvulsants: phenobarbital, phenytoin, primadone, carbamazepine
- Miscellaneous: codeine, methadone, mifepristone, estrogens and progestins (including oral contraceptives)
- Oral hypoglycemics: pioglitazone, rosigitazone

In vitro data also suggest that sirolimus is a substrate for CYP3A4. Therefore, substances that induce or inhibit CYP3A4 may alter the pharmacologic effects of sirolimus and should be used with CAUTION. These medications include (but are not limited to):

Inhibitors of CYP3A4:

- Antibiotics: clarithromycin, erythromycin, troleandomycin
- HIV: anti-retrovirals (delaviridine), protease inhibitors (ritonavir, indinavir, saquinavir, nelfinavir, amprenavir, lopinavir)
- Antifungals: itraconazole, ketoconazole, voriconazole, fluconazole
- Antidepressants: nefazodone, fluvoxaine
- Calcium channel blockers: verapamil, diltiazem
- GI: cimetidine, aprepitant
- Miscellaneous: grapefruit or its juice

Inducers of CYP3A4:

- Glucocorticoids: cortisone (> 50 mg), hydrocortisone (> 40 mg), prednisone (> 10 mg), methylprednisolone (> 8 mg), dexamethasone (> 1.5 mg)Anticonvulsants: phenytoin, carbamazepine, Phenobarbital, oxcarbazepine
- HIV: efavirenz, nevirapine
- Antibiotics: rifampin, rifabutin, rifapentine
- Miscellaneous: St. John's wort, modafinil

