Increased Effect/Toxicity: Cyclosporine may increase Sirolimus concentrations during concurrent therapy; Sirolimus should be taken 4 hours after cyclosporine oral solution (modified) and/or cyclosporine capsules (modified). CYP3A4 inhibitors may increase the levels/effects of Sirolimus. Refer to package insert for a list of CYP3A4 inhibitors.

Concurrent use of ACE inhibitors may increase the risk of angioedema. Concurrent live organism vaccines may increase the adverse/toxic effect of the vaccine; vaccinial infections are possible (avoid concurrent use).

Voriconazole may decrease the metabolism (via CYP isoenzymes) of Sirolimus (avoid concurrent use). Concurrent therapy with calcineurin inhibitors (cyclosporine, tacrolimus) may increase the risk of HUS/TTP/TMA.

Decreased Effect: CYP3A4 inducers may decrease the levels/effects of Sirolimus. Vaccination (dead organisms) may be less effective with concurrent sirolimus (monitor).

Ethanol/Nutrition/Herb Interactions:

Food: Do not administer with grapefruit juice; may decrease clearance of sirolimus. Ingestion with high-fat meals decreases peak concentrations but

increases AUC by 23% to 35%. Sirolimus should be taken consistently either with or without food to minimize variability.

15.27 **Known potential adverse events:** Consult the package insert for the most current and complete information.

Common or severe toxicity: Hypertension, edema, capillary leak syndrome, poor wound healing, hypertriglyceridemia, hypercholesterolemia, hypokalemia, constipation, diarrhea, dyspepsia, nausea and vomiting, deep venous and arterial thrombosis, abnormal liver function tests, hypersensitivity reaction, infection, sepsis, lymphoma, arthralgia, headache, renal failure, interstitial pneumonitis, pulmonary hemorrhage, thrombocytopenia and leukopenia.

15.28 **Drug procurement:** Commercial supplies. Pharmacies or clinics shall obtain supplies from normal commercial supply chain or wholesaler.

15.29 Nursing Guidelines:

15.291 Patients should be instructed that tablets should be swallowed whole, and not crush, split or chewed. If solution is used, it should be mixed with at least 2 ounces of water or orange juice. No other liquids should be used for dilution. Mixed solution should be drunk immediately, then add an additional 4 ounces of water or juice to the cup, stir vigorously and again drunk immediately.

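### Appendix IV allows voriconazole, and probably grapefruit juice, with caution during treatment, while Section 15.26 says to avoid them; St. John's wort (3.27) has a similar mismatch

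*Combined protocol and SAP*

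**What the plan says.** Section 15.26, on sirolimus interactions, gives the general warning that "CYP3A4 inhibitors may increase the levels/effects of Sirolimus" and refers the reader to the package insert for a list of inhibitors. It then singles out two agents. On the antifungal it says "Voriconazole may decrease the metabolism (via CYP isoenzymes) of Sirolimus (avoid concurrent use", the last words being a bracketed instruction. Under food interactions it says "Do not administer with grapefruit juice; may decrease clearance of sirolimus".

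The closing part of Appendix IV deals with the same enzyme and gives a softer instruction: "substances that induce or inhibit CYP3A4 may alter the pharmacologic effects of sirolimus and should be used with CAUTION". The inhibitors it then names include "Antifungals: itraconazole, ketoconazole, voriconazole, fluconazole" and "Miscellaneous: grapefruit or its juice". St. John's wort is among the inducers under the same instruction.

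Two exclusion criteria bear on this. Section 3.27 excludes patients using St. John's wort. Section 3.29 excludes patients who cannot stop potent CYP3A4 inhibitors or inducers, and points to Appendix IV.

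Appendix IV also has a list of drugs prohibited with sirolimus, one line of which reads "Immune modulators: cyclosporine, tacrolimus, sirolimus". Just before that list is a sentence stating that "there were no GW786034-related effects on the activities of" several CYP enzymes. Elsewhere the appendix leaves a placeholder where the study agent's name should stand.

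**The concern.** Avoiding a drug and using it with caution are different orders to a pharmacist or coordinator, and the protocol gives both for the same agent without ranking the two texts. The situation is realistic: a patient on treatment is prescribed an antifungal, staff open the drug-interaction appendix, and it permits voriconazole with caution. Section 15.26 gives the reason for the stricter rule, which is reduced metabolism or clearance of sirolimus and therefore higher exposure.

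The treatment plan has no early check on that exposure. Sirolimus starts at 5 mg daily in both phases (Section 7.1), the test schedule in Section 4.0 includes no sirolimus level, and the Section 8 dose changes are triggered by adverse events. What is at stake is the safety of individual patients.

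**Working it through.** No arithmetic applies, so the check sets the texts side by side.

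| Agent | Stricter text | Softer text | Reading |
|---|---|---|---|
| Voriconazole | 15.26: avoid concurrent use | Appendix IV: caution | Clear conflict, same drug and same period |
| Grapefruit juice | 15.26: do not administer sirolimus with it | Appendix IV: caution | Likely conflict |
| St. John's wort | 3.27: use is an exclusion | Appendix IV: caution | Similar mismatch, but 3.27 acts at entry |
| Cyclosporine | Appendix IV: prohibited | 15.26: give sirolimus 4 hours after it | Mismatch in the other direction |

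1. *Voriconazole.* Both texts concern use together with sirolimus during treatment. Staff who follow 15.26 satisfy both. Staff who follow Appendix IV alone may allow a drug that 15.26 says to avoid.

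2. *Grapefruit juice.* The 15.26 wording is under food effects and can be read narrowly, as not taking a dose with the juice. On that reading, general caution in the appendix is compatible with it. However, the reason given is reduced clearance, which suggests a concern beyond how the dose is swallowed. Sections 15.24 and 15.291 allow only water or orange juice as diluent, but they cover the oral solution and not tablets. The conflict is therefore likely rather than certain.

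3. *St. John's wort.* It is an inducer, so the expected effect is lower sirolimus levels. Section 3.27 keeps users out at entry, but the appendix would let an enrolled patient start it with caution.

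4. *Does 3.29 settle the matter?* It is a stricter rule and it points to Appendix IV. But it is an entry criterion and does not say what to do when a drug is prescribed in mid-treatment. It also depends on knowing which agents are potent, and the readable appendix does not mark them. The first table in Appendix IV is scrambled in the text available, so potency marks there cannot be ruled out.

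5. *Cyclosporine.* Appendix IV prohibits it. Section 15.26 gives a dosing interval, which presupposes joint use, and separately warns that calcineurin inhibitors may raise the risk of HUS/TTP/TMA.

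6. *Leftover text in Appendix IV.* There are three items: the sentence on GW786034, a code that appears nowhere else and is not a study drug; sirolimus on the list of drugs prohibited with sirolimus; and the unfilled study-agent placeholder. They are clerical and change no treatment decision.

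**The case against.** The best defence is that the two texts can both be obeyed: whoever follows 15.26 also satisfies Appendix IV, so this is a stricter and a looser warning and not a pair of irreconcilable orders. Staff sent to the appendix by 3.29 also arrive under a rule stricter than caution. Both statements are true, and they keep the point minor. They do not remove it, because obeying both texts requires having read both, and 3.29 stops at entry.

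It is also fair that the grapefruit wording may be only a dosing instruction. For that reason it is graded below voriconazole.

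A reader might go further and infer from the GW786034 sentence that the whole prohibited list was carried over from another compound and is wrong for sirolimus. That list is justified by a statement that sirolimus inhibits CYP2C9 most strongly. Section 15.26 mentions only weak CYP3A4 inhibition and says nothing either way about CYP2C9. The stray sentence stands next to the CYP2C9 statement, but position is not evidence that the statement is wrong. Comparing the list with the appendix's CYP3A4 tables would not help, since those tables concern a different enzyme. The documents do not support that inference, and it is not part of this point.

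**Conclusion.** The concern holds as a minor inconsistency in the concomitant-medication rules. Its extent is one clear conflict (voriconazole), one likely conflict (grapefruit juice), one related mismatch (St. John's wort) and one mismatch in the other direction (cyclosporine). The three leftover items are clean-up only.

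It is more than editorial for one reason: the appendix, followed as written, permits a drug that the protocol elsewhere says to avoid, in a trial with no scheduled sirolimus level. The conclusion assumes that some staff will consult the appendix without 15.26. The documents neither show nor exclude this, and they give no figure for the rise in exposure, so no effect on toxicity rates can be estimated.

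A reader might infer that the phase I dose finding or the phase II decision rule is compromised. Nothing in the documents supports that. Sample size, alpha and power are unaffected.

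**What to change.** In Appendix IV, move voriconazole, grapefruit juice and St. John's wort from the caution lists to avoid or prohibited during treatment. Add one sentence stating that where the appendix and Sections 15.26, 3.27 or 3.29 differ, the stricter instruction governs. Marking the potent CYP3A4 agents would also make 3.29 usable from the appendix.

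Reconcile cyclosporine. The simplest course is to keep the prohibition, give the HUS/TTP/TMA reason from 15.26 beside it, and note in 15.26 that the 4-hour interval does not apply in this trial.

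As clean-up, delete the GW786034 sentence and the sirolimus entry on its own prohibited list, and fill in the study-agent placeholder. Leave the other prohibitions as they are.

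The cost is a text correction within a protocol amendment. It adds no patients, procedures or analyses, and the statistical design does not change.
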